8.4.1.3 Tilmanocept Uptake Value (TUV)

TUV is a quantitative imaging metric used to characterize the amount of CD206 activity on planar imaging. Results from a prior Phase 1 and 2 study have demonstrated that TUV is a sensitive and specific predictor of visually interrogated Tc 99m tilmanocept localization in joint regions with presumed inflammatory macrophage activity. A per-joint TUV (TUV_{joint}) relative ratio will be calculated for the each of the 22 DAS-28 joints located in the hands and wrists. A subject-level global TUV (TUV_{global}) assessed across the 22 joints will be used as an indication of overall disease burden.

For all subjects, delegated trained imaging scientists blinded to all clinical subject information will perform semi-automated ROI drawing on whole body planar images and static images of the bilateral hands and wrists to derive relevant count statistics, which are input parameters for joint-specific (TUV_{joint}) and global (TUV_{global}) TUVs. TUV metrics are further described in the NAV3-31 Statistical Analysis Plan.

8.5 Adverse Events

8.5.1 Definition of Adverse Event

The definitions below follow International Conference on Harmonization (ICH) – Good Clinical Practice (GCP) (see also ICH Guideline for Clinical Safety Data Management: Definitions and Standards for Expedited Reporting).

An AE is defined as any untoward medical occurrence in a subject administered a pharmaceutical product and which does not necessarily have a causal relationship with this treatment. An AE can therefore be any unfavorable and unintended sign (including an abnormal laboratory finding), symptom, or disease temporally associated with the use of a medicinal (investigational) product, whether or not considered related to the medicinal (investigational) product.

Any clinically significant change in a condition (worsening) from screening that results in a change in subject management will be considered an AE and will be recorded on the AE page of the CRF.

By definition for this study, all untoward medical occurrences beginning on the Visit 2 (Day 0) until the final visit (variable per arm) are to be reported as AEs. AEs continuing after study completion will be followed to normalization or stabilization. Additionally, untoward medical events occurring prior to the day of Tc 99m tilmanocept administration will be collected and added to the subject's medical history unless they are related to a study procedure, in which case the event will be recorded as an AE. SAEs will be reported from the time of consent through the end of participation.

8.5.2 Categories for Adverse Event Assessment

The severity of an AE is classified according to the following categories, taking into account the possible range of the intensity of the event:

- Mild The adverse event is transient and easily tolerated by the subject.
- Moderate The adverse event causes the subject discomfort and interrupts the subject's usual activities
- Severe The adverse event causes considerable interference with the subject's usual activities and may be incapacitating or life-threatening.

Specific drug treatment

Any specific drug treatment will be documented.

Causal relationship to investigational product

The investigator will use the following definitions to assess the relationship of the adverse event to the use of investigational product:

Definitely related:	Event can be fully explained by administration of the investigational product.
Probably related:	Event is most likely to be explained by administration of the investigational product rather than the subject's clinical state or other agents/therapies.
Possibly related:	Event may be explained by administration of the investigational product or by the subject's clinical state or other agents/therapies.
Probably not related:	Event is most likely to be explained by the subject's clinical state or other agents/therapies, rather than the investigational product.
Definitely not related:	Event can be fully explained by the subject's clinical state or other agents/therapies.

For causality assessments, events meeting the categories of definitely, probably, or possibly related will be considered to be related to investigational product.

Causal relationship to study procedure

The investigator will use the following definitions to assess the relationship of the adverse event to study procedure:

Definitely related:	Event can be fully explained by the study procedure.
Probably related:	Event is most likely to be explained by the study rather than the subject's clinical state or other agents/therapies.
Possibly related:	Event may be explained by the study procedure or by the subject's clinical state or other agents/therapies.
Probably not related:	Event is most likely to be explained by the subject's clinical state or other agents/therapies, rather than the study procedure.
Definitely not related:	Event can be fully explained by the subject's clinical state or other agents/therapies.

For causality assessments, events meeting the categories of definitely, probably, or possibly related will be considered to be related to study.

8.5.3 Assessments and Documentation of Adverse Events

Attention shall be paid to the occurrence of AEs for the duration of subject participation. Events occurring prior to Visit 2 (Day 0) will be recorded in the subject's medical history unless related to study procedure, in which case the event will be recorded as an AE. Untoward medical events beginning on Visit 2 (Day 0) until the final visit (variable per arm) will be reported as adverse events.

Any AE (observed, volunteered, or elicited) should be recorded in detail in the source documentation.

The following information is required:

- The **date and time of onset** of any AE.
- The duration (the entire duration of an event or symptom, calculated from date of onset to date of end, if not recorded directly).
- The seriousness of the AE will be assessed by the investigator. If the investigator deems that an AE qualifies as an SAE, a special form provided by the sponsor should be completed and the event must be immediately reported to the sponsor. A definition of serious adverse events is provided in [Section 8.5.5](#).
- The maximum intensity (mild, moderate, or severe).
- Whether drug treatment was administered for the event, any specific drug treatment must be documented.
- The relationship of the AE to the investigational product and to study conduct (for definitions, see above).
- The **outcome** of the AE (resolved, resolved with sequelae, not resolved, unknown, death).

AEs will be coded according to an internationally recognized dictionary (Medical Dictionary for Regulatory Activities [MedDRA]).

8.5.4 Expected Adverse Events

Investigational Product-Related Risks

In all completed studies of Lymphoseek (Tc 99m tilmanocept), involving 553 subjects, only 3 events (breast pain and injection site pain reported by subjects with breast cancer and injection site irritation reported by a subject with head and neck squamous cell cancer) were deemed definitely related to the administration of Lymphoseek by the investigator. The most common adverse reactions (incident < 1%) have been lack of effect (< 0.067%), injection site pain (< 0.02%) and rash (< 0.02%). Adverse events from the radioactive dose are not expected, since the applied radiation doses are far below doses that can cause acute effects in human tissues.

In addition to the Lymphoseek pre-approval clinical studies, post-marketing surveillance shows that Lymphoseek has been administered to more than 250,000 patients with not a single drug-related SAE. Routes of administration included: subcutaneous, intradermal, and peritumoral.

The intended route of administration in this study is intravenous. There have been approximately 60 IV administrations of Tc 99m tilmanocept and no SAEs or ADRs have been reported to date.

Risks of Imaging Procedures

Radiation dose considerations from Tc 99m Tilmanocept planar and SPEC/CT scans – Patients enrolled in this trial will have whole body and hand/wrist planar gamma camera scans following Tc 99m Tilmanocept injection, with subjects enrolled in Arm 2 also receiving one hand/wrist SPECT/CT scan.

The average effective radiation dose per 10 mCi Tc 99m Tilmanocept injection is calculated to be 2.7 mSv (equivalent to about ten months of natural background radiation received in the US). Subjects enrolled in Arm 1 will receive one injection, equal to 2.7 mSv total; subjects enrolled in Arm 2 will receive a maximum of two injections plus one SPECT/CT scan- with an estimated effective dose of 1 mSv for the CT portion- amounting to 6.4 mSv total; subjects enrolled in Arm 3 will receive a maximum of four injections, equal to 10.8 mSv total. The maximum possible dose of ~10.8 mSv for any enrolled subject (no one will cross over into more than one study arm) is considered to be a moderate risk level corresponding to the benefit to the patient (category III based on the International Commission on Radiological Protection 62 (ICRP62)) and is balanced against the possible substantial societal benefit that can be gained from the trial (European Commission Radiation Protection 99, 1998 and ICRP 62, 1992). For further reference, the effective dose from a standard CT abdomen and pelvis, with and without contrast, is up to 20 mSv.

Precautionary Measures

Special precautionary measures are not considered necessary for this study. In case of emergency, standard emergency procedures will be employed.

Unexpected Adverse Events

An unexpected adverse event is defined as an adverse reaction that in nature and severity is not consistent with the applicable product information (e.g., Investigator's Brochure). Any adverse experience that is not listed in the current Investigator's Brochure or which is, with regard to the specificity or severity, not consistent with the risk information shall be regarded as unexpected.

Examples would be (a) acute renal failure listed in the Investigator's Brochure with a subsequent new report of interstitial nephritis and (b) hepatitis with a first report of fulminant hepatitis. "Unexpected" as used in this definition refers to an adverse drug experience that has not been previously observed and included in the Investigator's Brochure, rather than from the perspective of such experience not being anticipated from the pharmacological properties of the investigational product.

8.5.5 Serious Adverse Events

Definition of Serious Adverse Events

The following SAE definition is based on ICH guidelines and the final rule issued by the Food and Drug Administration (FDA) and effective 06 Apr 1998.

An SAE is classified as any untoward medical occurrence that at any dose:

- results in death, or
- is life threatening, or
- requires inpatient hospitalization or prolongation of existing hospitalization, or
- results in persistent or significant disability/incapacity, or
- is a congenital anomaly/birth defect, or
- is an important medical event (see paragraphs below).

The term 'life threatening' in the definition refers to an event in which the subject was at risk of death at the time of the event; it does not refer to an event that hypothetically might have caused death if it were more severe.

Medical and scientific judgment should be exercised in deciding whether it is appropriate to report an AE as serious also in other situations, such as important medical events that may not be immediately life threatening or result in death or hospitalization but may jeopardize the subject or may require intervention to prevent one of the other outcomes listed in the definition above. These should also usually be considered serious. Examples of such events are intensive treatment in an emergency room or at home for allergic bronchospasm or blood dyscrasias or convulsions that do not result in subject hospitalization.

Actions and reporting obligations in case of serious adverse events

The investigator should take appropriate diagnostic and therapeutic measures to minimize the risk to the subject.

If any SAE occurs over the course of the study, investigators or other site personnel will inform Navidea Biopharmaceutical representatives within 1 day (i.e., within 24 hours) of becoming aware of the SAE. Written notification of the SAE will be emailed to Navidea Biopharmaceuticals Pharmacovigilance at [contact]. For fatal or life-threatening adverse events where important or relevant information is missing, active follow-up is undertaken immediately.

Pregnancy will have the same time reporting obligations to the sponsor as SAEs. Upon notification, Navidea will provide a form for collection of pregnancy information.

All SAEs must also be recorded on the Adverse Event eCRFs.

Notification of the IRB(s)

The sponsor and/or the investigator will notify the IRB(s) about all relevant events (e.g., serious adverse events [SAEs] and Suspected, Unexpected, Serious Adverse Reactions [SUSARs]) according to all applicable regulations.

Notification of the authorities

The sponsor will process and report all relevant events (e.g., SAEs, SUSARs) to the authorities according to all applicable regulations.

Sponsor's notification of the investigators

The sponsor will inform all investigators about reported relevant events (e.g., SAEs, SUSARs) according to all applicable regulations.

8.6 Physical Examination

Complete physical examinations will be conducted at screening including height and weight assessments.

Physical examinations will be performed for the following body systems:

- General Appearance
- Skin/dermatological
- Eyes, ears, nose, throat
- Head and neck (including thyroid)
- Lungs
- Heart
- Abdomen (liver, kidney, spleen, gastrointestinal)
- Lymph nodes
- Musculoskeletal
- Nervous system

8.7 Vital Signs

Vital signs comprise the measurement of body temperature, heart rate, respiration, systolic and diastolic blood pressure. All measurements will be taken after the subject has been in a resting position for at least 1 minute. Vital signs will be measured at screening, within 30 minutes before investigational product injection, and within 30 minutes post injection. Any clinically significant change from screening (worsening) that results in a change in subject management will be considered an AE and will be recorded on the AE page of the CRF.

8.8 Electrocardiogram

A standard 12-lead electrocardiogram (ECG) will be obtained up to 30 minutes before investigational product administration and within 30 minutes after investigational product administration. The ECG will be measured with the subject in a resting position for at least 1 minute. Continuous ECG monitoring is not required. At a minimum, the heart rate, QRS, PR and QT intervals will be collected. QTc will be calculated using the Fridericia formulas.

On-site investigator's responsibilities

The immediate cardiac safety of the subject will be ensured by the on-site qualified physician. Any 12-lead ECG intervals, waveform abnormalities, and rhythm changes that are clinically significant in that they result in a change in subject management will be considered an AE. In the case of an SAE, once SAE notification is decided upon, investigators are required to follow the procedure described for SAE notification and document abnormal ECG findings (intervals and waveforms). Any interval data or abnormal waveform finding that resulted in an AE (i.e., change of patient management) must be followed to normalization or stabilization. Each 12-lead ECG tracing must be signed and dated and stored in the subject's source documentation.

8.9 Clinical Laboratory Parameters

Table 12 Clinical Laboratory Parameters

Hematology	Hemoglobin (Hgb), hematocrit (HCT), platelets, neutrophils, basophils, lymphocytes, monocytes, red blood cells (RBC), white blood cells (WBC)
Serum chemistry	Aspartate aminotransferase (AST), alanine aminotransferase (ALT), alkaline phosphatase, total bilirubin, creatinine, chloride, potassium, sodium, total protein, albumin, carbon dioxide (CO ₂)/bicarbonate, blood urea nitrogen (BUN), glucose
Urinalysis	pH, specific gravity
Rheumatoid Panel	Erythrocyte sedimentation rate (ESR), C-reactive protein (CRP), rheumatoid factor (RF); anti-citrullinated peptide antibody (ACPA)

All laboratory reports must be promptly reviewed for clinical significance by the investigator, and upon review, initialed and dated by the investigator.

Good clinical practice would suggest that a copy of the laboratory results also be provided to the subject's referring physician.

Only abnormal laboratory values will be collected in the electronic database. Any change in a laboratory value, which results in a change in subject management (additional controls or treatment required), will be reported as a clinically significant change. Clinically significant changes in laboratory parameters, which are not the result of laboratory error, are to be recorded as AEs.

Any clinically significant changes in laboratory values are to be followed up with repeated tests at appropriate intervals (as determined by the investigator) until the values return to baseline level or until the abnormality is explained by the investigator. The expected amount of blood to be drawn is shown in [Table 13](#).

Table 13 Approximate Amount of Blood Drawn per Subject by Study Arm

Arm	Timepoint	Test (Sample Volume)	Total Blood Drawn at Timepoint
1	Visit 1 (Day -30 to -1)	Chemistry (5 mL)	
		Hematology (4 mL)	13 mL (2.6 teaspoons)
		RA panel (4 mL)	
2	Visit 2 (Day 0)	Chemistry (5 mL)	
		Hematology (4 mL)	9 mL (1.8 teaspoons)
		Total (Arm 1) 22 mL (4.5 teaspoons)	
2	Visit 1 (Day -30 to -1)	Chemistry (5 mL)	
		Hematology (4 mL)	13 mL (2.6 teaspoons)
		RA Panel (4 mL)	
3	Visit 2 (Day 0)	Chemistry (5 mL)	
		Hematology (4 mL)	9 mL (1.8 teaspoons)
		Total (Arm 2) 31 mL (6.3 teaspoons)	
3	Visit 1 (Day -30 to -1)	Chemistry (5 mL)	
		Hematology (4 mL)	13 mL (2.6 teaspoons)
		RA panel (4 mL)	
3	Visit 2 (Day 0)	Chemistry (5 mL)	
		Hematology (4 mL)	9 mL (1.8 teaspoons)
		Total (Arm 3) 61 mL (12.4 teaspoons)	
3	Visit 4 (5 ± 1 weeks after initiation of new anti-TNF α bDMARD therapy)	Chemistry (5 mL)	
		Hematology (4 mL)	13 mL (2.6 teaspoons)
		RA panel (4 mL)	
3	Visit 6 (12 ± 1 weeks after initiation of new anti-TNF α bDMARD therapy)	Chemistry (5 mL)	
		Hematology (4 mL)	13 mL (2.6 teaspoons)
		RA panel (4 mL)	
3	Visit 8 (24 ± 1 weeks after initiation of new anti-TNF α bDMARD therapy)	Chemistry (5 mL)	
		Hematology (4 mL)	13 mL (2.6 teaspoons)
		RA panel (4 mL)	

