2.3 Safety Objective(s)

- To evaluate safety through the examination of AE incidence and changes over time in laboratory tests, vital signs, and physical examination findings.

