9.5.4 Analysis of Safety Variables

All safety analyses will be conducted on the safety population.

All AEs will be observed for each subject from the time of signing of informed consent until study completion. A treatment-emergent AE (TEAE) is defined as an AE whose start date is on or after the initial procedure date. If the procedure date or the AE start date is missing, the AE will be considered treatment emergent.

Prior to analysis all AEs will be coded using the MedDRA coding dictionary. Based on the coded terms, TEAEs will be summarized by cohort and overall as follows:

- By system organ class (SOC) and preferred term (PT);
- By SOC and PT and relation to the study drug;
- By SOC and PT and severity.

Observed and change from baseline vital sign parameters, ECG parameters and hematology, clinical chemistry and urinalysis parameters will be summarized using descriptive statistics (mean, standard deviation, median, and range) for each Arm and overall at each time point.

Other safety analyses may be described in the SAP for the study.

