5.2 Description of Safety Analysis

The following describes the safety analyses to be performed for the study. All safety analyses will be performed on the safety population. Follow up timing will vary by arm as noted above.

Adverse Events

Adverse events will be observed for each subject from signing of informed consent until termination from the study. AEs will be coded using the Medical Dictionary for Regulatory Activities (MedDRA®). A treatment-emergent AE (TEAE) is defined as an AE whose start date is on or after the initial procedure date. Based on the coded terms, frequencies of each TEAE will be summarized

by MedDRA® preferred term within system organ class (SOC), by severity grade, and by relationship to Tc 99m Tilmanocept for each arm and overall.

A summary of TEAEs will be constructed showing the following by arm and overall:

- Number of subjects with at least one TEAE
- TEAEs by arm and severity grade
- TEAE by arm and relationship to Tc 99m tilmanocept
- TEAEs by arm and relationship of TEAE to study procedure
- Number of subjects with at least one treatment emergent serious adverse event

Treatment-emergent serious adverse events (TESAEs) will be tabulated by MedDRA® preferred term within SOC by arm and overall.

A by-patient AE data listing of all AEs including verbatim term, coded term, grade, and relation to study drug will be provided.

Clinical Laboratory Tests

Clinical laboratory tests will be performed at screening (baseline) and after the final image acquisition on each imaging day. Only abnormal laboratory values and RA lab values will be assessed for clinical significance as applicable. For each quantitative laboratory test, summary statistics (mean, standard deviation, median, range, n) on the raw as well as their changes from baseline will be presented by timepoint by arm and overall. A shift table will also be produced to show the changes in lab values over time relative to the normal ranges.

If multiple labs were performed at a given visit, then the latest results will be summarized in the analysis tables. All collected lab data will be listed.

ECG Parameters

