	Low/ Low	Low/ Normal	Low/ High	Normal/ Low	Normal/ Normal	Normal/ High	High/ Low	High/ Normal	High/ High	
xxxxxxxxx/ xxxxxxxxxx (xxx)	xxx (xxx%)	xxx (xxx%)	xxx (xxx%)	xxx (xxx%)	xxx (xxx%)	xxx (xxx%)	xxx (xxx%)	xxx (xxx%)	xxx (xxx%)	xxx (xxx%)
xxxxxxxxx/ xxxxxxxxxx (xxx)	xxx (xxx%)	xxx (xxx%)	xxx (xxx%)	xxx (xxx%)	xxx (xxx%)	xxx (xxx%)	xxx (xxx%)	xxx (xxx%)	xxx (xxx%)	xxx (xxx%)
xxxxxxxxx/ xxxxxxxxxx (xxx)	xxx (xxx%)	xxx (xxx%)	xxx (xxx%)	xxx (xxx%)	xxx (xxx%)	xxx (xxx%)	xxx (xxx%)	xxx (xxx%)	xxx (xxx%)	xxx (xxx%)
xxxxxxxxx/ xxxxxxxxxx (xxx)	xxx (xxx%)	xxx (xxx%)	xxx (xxx%)	xxx (xxx%)	xxx (xxx%)	xxx (xxx%)	xxx (xxx%)	xxx (xxx%)	xxx (xxx%)	xxx (xxx%)

^a HC = Healthy Control, RA-2 = Rheumatoid Arthritis (stable treatment regimen), RA-3 = Rheumatoid Arthritis (candidate for changed treatment).

STATKING Clinical Services (DD-MMM-YYYY)

Source Program: xxxxxxxx.sas

Table format is repeated for Tables 37 (Hematology) and 38 (Urinalysis)

Table 36. Serum Chemistry Clinical Laboratory Parameters Shift Table by Arm
Navidea Biopharmaceuticals - Study No. NAV3-31
Safety Population (N=xxxx)

Part 2 of 7: Arm 2 RA-2^a - Day 0

Panel/Parameter (units)	Baseline Result/ Post-Injection Result									
	Low/ Low	Low/ Normal	Low/ High	Normal/ Low	Normal/ Normal	Normal/ High	High/ Low	High/ Normal	High/ High	
xxxxxx/	xxx (xxx%)	xxx (xxx%)	xxx (xxx%)	xxx (xxx%)	xxx (xxx%)	xxx (xxx%)	xxx (xxx%)	xxx (xxx%)	xxx (xxx%)	xxx (xxx%)
xxxxxxx (xxx)	xxx (xxx%)	xxx (xxx%)	xxx (xxx%)	xxx (xxx%)	xxx (xxx%)	xxx (xxx%)	xxx (xxx%)	xxx (xxx%)	xxx (xxx%)	xxx (xxx%)
xxxxxx/	xxx (xxx%)	xxx (xxx%)	xxx (xxx%)	xxx (xxx%)	xxx (xxx%)	xxx (xxx%)	xxx (xxx%)	xxx (xxx%)	xxx (xxx%)	xxx (xxx%)
xxxxxxx (xxx)	xxx (xxx%)	xxx (xxx%)	xxx (xxx%)	xxx (xxx%)	xxx (xxx%)	xxx (xxx%)	xxx (xxx%)	xxx (xxx%)	xxx (xxx%)	xxx (xxx%)
xxxxxx/	xxx (xxx%)	xxx (xxx%)	xxx (xxx%)	xxx (xxx%)	xxx (xxx%)	xxx (xxx%)	xxx (xxx%)	xxx (xxx%)	xxx (xxx%)	xxx (xxx%)
xxxxxxx (xxx)										

^a HC = Healthy Control, RA-2 = Rheumatoid Arthritis (stable treatment regimen), RA-3 = Rheumatoid Arthritis (candidate for changed treatment).

STATKING Clinical Services (DD-MMM-YYYY)

Source Program: xxxxxxx.sas

Table format is repeated for Tables 37 (Hematology) and 38 (Urinalysis)

Table 36. Clinical Laboratory Parameters Shift Table by Arm
 Navidea Biopharmaceuticals - Study No. NAV3-31
 Safety Population (N=xxx)

Part 3 of 7: Arm 2 RA-2^a - Day 8

Panel/Parameter (Units)	Baseline Result/ Post-Injection Result									

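### Protocol 8.9 keeps only abnormal laboratory values in the database, which conflicts with the planned laboratory means, changes from baseline and shift tables; the passages must be reconciled.

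*Protocol*

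**What the plan says.** Protocol 8.9, below the list of analytes in Table 12, sets the collection rule: "Only abnormal laboratory values will be collected in the electronic database". It makes no exception by panel, arm or visit.

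The analysis sections assume more than that:

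- Protocol 2.3 gives the safety objective: "To evaluate safety through the examination of AE incidence and changes over time in laboratory tests, vital signs, and physical examination findings".
- Protocol 9.5.4: "Observed and change from baseline vital sign parameters, ECG parameters and hematology, clinical chemistry and urinalysis parameters will be summarized using descriptive statistics", by arm and time point.
- SAP 5.2 asks, for each quantitative test, for "summary statistics (mean, standard deviation, median, range, n) on the raw as well as their changes from baseline", and adds: "A shift table will also be produced to show the changes in lab values over time relative to the normal ranges".
- The SAP Appendix B shells carry this through. Table 33 (repeated for 34 and 35) has screening-baseline rows and change-from-baseline rows. Table 36 (repeated for 37 and 38) has nine baseline-by-post-injection columns, including "Normal/ Normal".

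Three other places bear on the point. SAP 2.3 allows no imputation and uses observed data only. Protocol 10.1.1 says in general terms that eCRFs are the vehicle for all trial data, and leaves completion details to a separate document. SAP 5.2 has its own sentence about abnormal values: "Only abnormal laboratory values and RA lab values will be assessed for clinical significance as applicable".

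**The concern.** A mean, a change from baseline or a shift from normal to high can be computed only if normal results are in the database. A rule that discards them makes inclusion in the summary depend on the value being summarised. The result is a selected sample, and no imputation is planned that could repair it.

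At stake are SAP Tables 33-38, the planned laboratory summaries for a stated safety objective. A reader of the study report would take them to describe each arm, when they would describe only subjects outside the reference range.

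The rule also reaches the rheumatoid panel, which is part of Table 12. ESR enters DAS28 and the ACR response. Baseline ACPA drives prediction algorithms 3, 6 and 7 in SAP 4.2.2 and is summarised on a continuous scale in Table 66. Both are needed whether or not the result is normal.

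**Working it through.** The plan states no figure to reproduce. The check is textual first, then illustrative.

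**Step 1: the rule against the tables.**

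- Raw summaries (Tables 33-35): under 8.9 every recorded value lies outside its reference range, so n, mean and SD refer to abnormal results only.
- Change from baseline: this needs two recorded values in the same subject, so both must be abnormal.
- Shift tables (Tables 36-38): there are 3 × 3 = 9 cells. Those involving Normal are Low/Normal, Normal/Low, Normal/Normal, Normal/High and High/Normal, which is 5 of 9. None of the five can be filled from recorded values. Only Low/Low, Low/High, High/Low and High/High remain.
- Blanks: a blank can be classed as normal only if the eCRF separately records that the test was done. Otherwise normal and not done look alike, and the denominators are undefined.

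**Step 2: how many subjects would have a computable change.** The arm sizes, 38, 38 and 29, come from Protocol 9.4. The rest is assumed, because the documents give neither an abnormal rate nor a correlation. Baseline and post-injection values are taken as bivariate standard normal with correlation ρ and no true shift. A value is abnormal when |z| > c, with c = z(1 − p/2) and p the share of values that are abnormal.

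Expected number with a recorded baseline = 38 × p. Expected number with a computable change = N × P(both abnormal). With 1,000,000 simulated pairs per setting, P(both abnormal) at ρ = 0.5 / 0.7 / 0.9 was 0.0094 / 0.0165 / 0.0295 for p = 5%, 0.0244 / 0.0390 / 0.0639 for p = 10%, and 0.0663 / 0.0938 / 0.1376 for p = 20%.

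| p | Baseline recorded, of 38 | Change computable, of 38 (ρ = 0.5 / 0.7 / 0.9) | Change computable, of 29 | True share normal at both visits |
|---|---|---|---|---|
| 5% | 1.9 | 0.36 / 0.63 / 1.12 | 0.27 / 0.48 / 0.86 | 90.9 / 91.7 / 93.0% |
| 10% | 3.8 | 0.93 / 1.48 / 2.43 | 0.71 / 1.13 / 1.85 | 82.5 / 83.9 / 86.4% |
| 20% | 7.6 | 2.52 / 3.56 / 5.23 | 1.92 / 2.72 / 3.99 | 66.6 / 69.4 / 73.8% |

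For example, 38 × 0.0094 = 0.36 and 38 × 0.1376 = 5.23.

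**Step 3: selection biases as well as thins.** With a true shift of 0.5 SD in the same model, the mean recorded change was 0.17 to 0.34 SD at p = 5% and 0.27 to 0.37 SD at p = 20%, against a truth of 0.50.

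**Step 4: the direction of distortion in the raw means depends on the model.** In the symmetric model with no true shift, the recorded values have mean near 0, and SD about 2.4 times the true SD at p = 5% and 1.8 times at p = 20%. If only high values count as abnormal, with a 2.5% tail, the mean is φ(1.96)/0.025 = 0.0584/0.025 ≈ 2.3 SD and the variance is 1 + 1.96 × 2.338 − 2.338² ≈ 0.116, so the SD is about 0.34. An extreme mean and an inflated SD do not arise together in either no-shift case.

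**The case against.** The best defence is that the trial may well collect everything. Protocol 10.1 and 10.1.1 have required data entered on eCRFs without a laboratory exception. The SAP, written later, words the abnormal-only idea as a limit on assessing clinical significance. The shift shells and Data Listings 12-15, with result, reference range and a significance flag, look designed for full data. This stands as evidence of what the analyst expects. It does not settle the matter: 8.9 is the specific rule, 10.1.1 is general, the SAP promises to list only what was collected, and the SAP declares itself consistent with protocol Amendment 4. The eCRF is not among the documents.

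It can also be said that the shift tables survive if the eCRF records that a panel was run, since an unrecorded result could then be classed as normal. That is right, so a reader should not infer that the cell for normal at both visits must print zero. For ALT, AST and glomerular filtration rate a missing baseline is also unlikely, because eligibility depends on them.

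Two stronger inferences are tempting. One is that the means would be extreme; Step 4 shows that this depends on whether abnormality is one-sided. The other is that the study could neither show nor exclude a laboratory effect. New abnormal values would still be recorded and listed, and 8.9 makes clinically significant changes adverse events with repeat testing. Nor would complete means isolate a tracer effect in Arm 3 after Day 0: there is no randomised control, and those subjects start a new anti-TNFα agent.

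Finally, a 5% abnormal rate is not assured in treated RA patients. That is fair, and is why the table runs to 20%.

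**Conclusion.** The conflict is real and should be resolved. Protocol 8.9 cannot stand beside 9.5.4, 10.1.1, SAP 5.2 and the laboratory shells. If 8.9 governs, Tables 33-38 are selected and misleading as summaries of change over time. That part follows from the text without any assumption.

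The size does rest on assumptions. In the normal model, the number of subjects with a computable change runs from 0.4-1.1 of 38 at 5% abnormal to 2.5-5.2 of 38 at 20%, so the change summaries are unusable across that range. Whether the harm occurs depends on an eCRF that the documents do not show. The documents do not support going further, to extreme means or to a study blind to laboratory effects. Sample sizes and the primary TUV precision analyses in Arms 1 and 2 are unaffected.

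**What to change.** Amend Protocol 8.9 so that every Table 12 result, rheumatoid panel included, is entered at each scheduled visit with units and reference range. Keep the abnormal-only restriction for the assessment of clinical significance, in line with SAP 5.2, which also includes RA values in that assessment.

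- If the eCRF already captures all results, correct the sentence in 8.9 and leave the tables alone.
- If normal values were not entered and will not be recovered, replace the means, changes and shift tables in Tables 33-38 with counts of abnormal values over subjects tested, plus the listings. This needs a record of which tests were done.

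No extra samples are required; the results exist and the investigator already reviews each report. The cost is a protocol amendment and data entry at up to 10 centers. Some entry may be retrospective, since SAP 2.4 reports interim analysis 3 as already performed. The documents describe no central laboratory, so a single electronic transfer should not be assumed.
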